#### Suggestions for Rash Management [Lacouture 2011, Kiyohara 2013, www.psoriasis.org]

#### Papulopustular (acneiform) rash:

- Most common rash seen with EGFR inhibitors
- Typically seen in the first few weeks of treatment
- Usually peaks at Week 4–6
- Then will decrease in severity at Week 6–8
- Post-inflammatory skin changes can last for months, so prevention and reactive treatment are important

#### Suggestions for preventative treatment:

- Patient education prior to starting treatment on what to expect
- Gentle cleansing of skin using mild soap products
- Use of moisturizer twice daily making sure to include hands, feet and nails
- Avoid sun when possible and use of sunscreen SPF 30 or higher (preferably titanium dioxide or zinc oxide)
- Hypoallergenic makeup when possible

#### Suggestions for treatment once a rash appears (see Appendix 5 for steroid potency chart):

- Ongoing use of treatments from 'preventative treatments' above
- Grade 1 (<10 % BSA involved, without pruritus or tenderness)
  - Topical steroids (refer to Appendix 5 for a steroid potency chart that categorizes brand name topical steroid medications)
    - For face use medium potency
    - For body use strong potency
    - Note: As soon as rash improves the lowest strength steroid that controls rash should be used, especially on the face
- Grade 2 (10%–30% BSA involved, ± pruritus/tenderness; limiting instrumental ADLs and causing psychosocial impact)
  - Topical steroids
    - $\circ$  For face use strong potency
    - For body use very strong potency
    - Note: As soon as rash improves the lowest strength steroid that controls rash should be used, especially on the face
  - Systemic treatment

- Doxycycline 100 mg BID (less renal toxic than minocycline, but can cause photosensitivity)
- Grade 3 (> 30% BSA involved, limiting ADLs)
  - Refer to dermatology
  - Topical steroids
    - All areas very strong potency
    - Note: As soon as rash improves the lowest strength steroid that controls rash should be used, especially on the face
  - Systemic treatment
    - Doxycycline 100 mg BID
    - Oral steroids: prednisolone 10 mg QD for 1 week or equivalent

#### **Suggestions for once a rash reappears:**

- Over the course of treatment rash may come and go
  - Hydrocortisone 1% cream with moisturizer and sunscreen twice daily, in combination with doxycycline 100 mg BID
  - May need to follow guidelines above if rash worsens

If unacceptable rash recurs on reintroduction of tesevatinib at the same dose, then dose reduction of tesevatinib should be discussed with the Medical Monitor.

### 9.1.4.3. QT Interval Prolongation

Patients should be carefully monitored for symptoms of arrhythmia (i.e., dyspnea, chest pain or tightness, palpitations, dizziness) and for episodes of syncope. An ECG should be obtained if these symptoms occur. In addition, serum potassium and magnesium must be maintained within the normal range and may require additional monitoring or adjustment if patients develop diarrhea. Medications with potential for QTc(F) prolongation should not be used concurrently or started within 24 hours of tesevatinib administration (see Appendix 4).

### 9.1.4.3.1. Management of QTc(F) Interval Prolongation

The following guidelines should be used in the management of QTc(F) prolongation. Patients will have ECGs performed at times designated by the protocol (refer to Table 1).

### Grade 2 QTc(F) Prolongation:

If the QTc(F) interval increases to an absolute value of  $\geq 60$  msec above baseline (predose on Day 1) but < 500 msec and the patient is asymptomatic (does not have palpitations, dizziness, syncope, orthostatic hypotension, or a significant ventricular arrhythmia on ECG), the following actions should be taken:

- Re-check and confirm concomitant medications for any medications that may be contributing to QTc(F) prolongation. Consult the Medical Monitor for discontinuation of any medication found.
- Check electrolytes, especially magnesium and potassium; correct abnormalities as clinically indicated.

### Grade 3 QTc(F) Prolongation:

If the QTc(F) interval increases to an absolute value of  $\geq$  500 msec at any evaluation and if the patient is asymptomatic (does not have palpitations, dizziness, syncope, orthostatic hypotension, or a significant ventricular arrhythmia on ECG), then the following actions should be taken:

- Consult with Medical Monitor
- Hold study drug
- Re-check and confirm concomitant medications for any medications that may be contributing to QTc(F) prolongation. Consult Medical Monitor for discontinuation of any medication found.
- Check electrolytes, especially magnesium and potassium; correct abnormalities as clinically indicated
- Contact Medical Monitor to discuss appropriate management
- **QTc(F)**: When QTc(F) is within 30 msec of baseline or ≤ 470 msec (whichever is lower), then study drug may be restarted with one dose level reduction.
- Following dose reduction and resumption of study drug treatment, ECGs must be repeated weekly for 2 weeks, then on Day 1 of each cycle per protocol following restart of study drug.
- Study drug may be restarted at the pre-event dose level if QTc(F) values of  $\geq 500$  msec are not confirmed by the central lab and if there is no evidence of drug-related abnormal ECG findings. This may be done as soon as the data are confirmed.

### Grade 4 QTc(F) Prolongation:

If the QTc(F) interval increases to an absolute value of  $\geq 500$  msec at any evaluation, and if the patient is or has recently been symptomatic (has palpitations, dizziness, syncope, orthostatic hypotension, a significant ventricular arrhythmia on ECG), then the following actions should be taken:

- The patient should be hospitalized and undergo a thorough cardiology evaluation
- Do not dose with study drug again
- Consult with Medical Monitor
- Check electrolytes especially magnesium and potassium; correct abnormalities as clinically indicated

• ECGs should be monitored until the QTc(F) returns to within 30 msec above the average baseline value or  $\leq$  470 msec

Study drug should be permanently discontinued if the cardiac/electrophysiology evaluation confirms that symptoms are the consequence of a drug-induced QTc(F) interval prolongation. However, if the patient has objective tumor response, consideration will be given to continuing treatment with tesevatinib at a reduced dose after discussion with the Medical Monitor.

### 9.1.4.4. Elevated Serum Creatinine

Patients with increases in serum creatinine to  $> 2 \times ULN$  should be evaluated for non-renal causes of renal dysfunction, such as dehydration due to diarrhea. Cystatin C values should also be utilized to evaluate renal function. Dose interruptions and reductions are not necessary in the absence of renal dysfunction.

### 9.1.4.5. Elevated Serum Amylase

In the event of asymptomatic increase of serum amylase to  $> 1.5 \times ULN$ , lipase, fasting triglycerides, and amylase isoenzymes should be monitored. Treatment should only be interrupted if clinical pancreatitis develops, corresponding to Grade 3 CTCAE per Table 5.

### 9.1.4.6. Interstitial Lung Disease

New or worsening respiratory symptoms suspicious of pneumonitis in patients in the study should be evaluated with high-resolution CT of the chest to determine whether ILD is present. Tesevatinib should be discontinued if interstitial lung disease is suspected, and further management discussed with the Medical Monitor.

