### 9.1.3. Dose Modifications and Delays for Toxicity Related to Study Drug

Patients who develop  $\geq$  Grade 3 adverse event(s) considered by the investigator to be related to study drug (with the exceptions noted below) will have study treatment interrupted until all drug-related toxicities have resolved to  $\leq$  Grade 1. Once these toxicities have resolved to  $\leq$  Grade 1, the patient may resume study treatment at a reduced dose of 250 mg/day. No more than one dose reduction is permitted. Patients who require more than one dose reduction will have study drug discontinued and enter the Follow-up Period.

The exceptions are:

- asymptomatic Grade 3 elevations of amylase or lipase,
- Grade 3 elevation of alkaline phosphatase in a patient known to have bone metastases,
- Grade 3 elevation of glucose in a patient receiving systemic corticosteroids,
- Grade 3 creatine phosphokinase [CPK] elevation in the absence of muscle symptoms,
- Grade 3 sodium values  $\geq 126 \text{ mmol/L}$  in a patient with diarrhea)

Patients for whom toxicity persists beyond 21 days despite dose interruption may resume study treatment at a reduced dose of 250 mg/day only with permission from the responsible Medical Monitor.

If study treatment is withheld, the patient should be instructed not to make up the withheld doses.

T٤	ıb	le	5	:

ed AEs

Occurrence	Grade 1	Grade 2	Grade 3	Grade 4

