First appearance	
 
No action with study drug
 
For diarrhea start loperamide, monitor for dehydration
 
For rash start topical steroids (see Section 9.1.4.2)
 
For QTc prolongation no action
 
	
 
No action with study drug
 
For diarrhea start/increase loperamide, monitor for dehydration
 
For rash topical steroids ± doxycycline (see Section 9.1.4.2)
 
For QTc check con-meds and electrolytes, correct as indicated
 
For confirmed pneumonitis interrupt and consult Medical Monitor
 
	
 
Interrupt treatment until resolved to Grade 0-1. If interruption < 21 days restart at 250 mg/day. If interruption ≥ 21 days, check with Medical Monitor.
 
In addition, for QTc check con- meds, electrolytes and consult Medical Monitor (see Section 9.1.4.3.1 for restarting and monitoring instructions).
 
For creatinine in absence of renal dysfunction no interruption.
 
	Discontinue. Consult Medical Monitor if continuation is in patient's best interest. In addition, for QTc hospitalize patient and perform cardiology evaluation (see Section 9.1.4.3.1)
appearance			drug	drug

# 9.1.3.1. Requirements for Continuation of Treatment Post Cycle 1

Patients must fulfill the following criteria in order to commence a new cycle of treatment:

- all related  $\geq$  Grade 3 AEs have resolved to  $\leq$  Grade 1
- serum potassium and magnesium above the lower limit of normal
- no arrhythmias, pathologic bradycardia, or associated symptomology
- $QTcF \le 470$  msec and increase from baseline  $\le 60$  msec unless Medical Monitor has given permission to continue
- no concurrent medications that prolong QTc (see Appendix 4)
- no evidence of progressive disease
- no additional therapeutic interventions for glioblastoma
- no strong inhibitors or inducers of CYP3A4, CYP2C8, CYP2D6 or CYP1A2 (see Appendix 4)

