# 11.5. Safety Monitoring

Patients will be closely monitored for adverse events of interest and potential drug-drug interactions through standard safety reporting as well as a regular medical review of safety data outputs from both the clinical and pharmacovigilance databases. Particular attention will be paid to the success of diarrhea and rash management strategies and the use of concomitant medications which have a risk of drug-drug interaction or QTc prolongation. SAEs, including deaths, and withdrawals due to adverse events will also be closely monitored. A central laboratory will be used to monitor for QTc prolongation, and any study drug reintroduction in the case of QTc prolongation will only be performed with the agreement of the Medical Monitor.

A Data Monitoring Committee will not be used for this study.

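### Section 9.1.4.6 stops tesevatinib when ILD is suspected at any grade, but the Section 9.1.3 dose table takes no drug action at Grade 1 and at Grade 2 only interrupts, once pneumonitis is confirmed

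*Protocol*

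**What the plan says.** Section 9.1.4 lists ILD among the adverse events of special interest. Section 9.1.4.6 sends respiratory symptoms that raise suspicion of pneumonitis to high-resolution chest CT, then adds: "Tesevatinib should be discontinued if interstitial lung disease is suspected, and further management discussed with the Medical Monitor". The action depends on suspicion and not on the CT result, and no grade or duration is attached.

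The dose-adjustment table in Section 9.1.3 covers the same event by CTCAE grade. In its first-appearance row, the Grade 1 and Grade 2 cells both open with "No action with study drug". The Grade 2 cell alone then adds "For confirmed pneumonitis interrupt and consult Medical Monitor". The Grade 3 cell interrupts until the event falls to Grade 0-1. For an interruption under "21 days restart at 250 mg/day"; for one of at least "21 days, check with Medical Monitor".

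The text of Section 9.1.3 follows the same pattern. Once toxicity has resolved to Grade 1 or less, "the patient may resume study treatment at a reduced dose of" 250 mg/day. If toxicity lasts beyond 21 days, the patient may resume "only with permission from the responsible Medical Monitor". ILD is not among the listed exceptions.

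For QTc prolongation, Section 11.5 has a separate safeguard: "any study drug reintroduction in the case of QTc prolongation will only be performed with the agreement of the Medical Monitor". It has no counterpart for ILD.

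**The concern.** The two instructions meet in the interval between first suspicion and the CT result. Section 9.1.4.6 stops the drug in that interval. Read alone, the table lets dosing continue at Grades 1 and 2.

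The question can come up more often than confirmed ILD does, because Section 5.2 lists cough and dyspnea among the most frequently reported adverse events. That frequency may not carry over to this trial. Section 5.2 describes most of the patients with malignancies treated at 300 mg daily or more, or 350 mg intermittently, as having advanced metastatic NSCLC. Section 11.5 says there is no Data Monitoring Committee, so the Medical Monitor step carries more weight.

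**Working it through.** The plan gives no figure to reproduce. The check is a comparison of the two instructions, followed by a rough count of how often ILD might occur.

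**Instruction by grade, first appearance**

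| Situation | Section 9.1.4.6 | Dose table, Section 9.1.3 |
|---|---|---|
| Suspected, Grade 1 | Discontinue; Medical Monitor | No drug action |
| Suspected, Grade 2 | Discontinue; Medical Monitor | No drug action |
| Suspected, Grade 3 | Discontinue; Medical Monitor | Interrupt; restart at 250 mg/day if under 21 days |
| Confirmed, Grade 1 | Stopped since suspicion | No drug action |
| Confirmed, Grade 2 | Stopped since suspicion | Interrupt; Medical Monitor |
| Confirmed, Grade 3 | Stopped since suspicion | Interrupt; restart at 250 mg/day if under 21 days |

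At Grade 4 the table discontinues, so there is no conflict over stopping. The comparison is confined to the first-appearance row because the later row is damaged in the text available for review.

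The table shows two differences at Grades 1 and 2:

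1. *Trigger.* Suspicion in one place, confirmation in the other. The Grade 1 cell has no pneumonitis line at all, so confirmation changes nothing there.
2. *Action.* Discontinue in one place, interrupt in the other.

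**Which instruction governs?** Section 5.2 sends the reader to Section 9.1.4 for managing events of special interest, which favours Section 9.1.4.6. Section 7.1 sends the reader to Section 9.1.3 for dose interruptions and reductions. The table's rash and QTc entries cite their own subsections of 9.1.4, but its pneumonitis line cites none. The *unless otherwise specified* clause in Section 9.1.4 qualifies only the investigator's 21-day hold. Nothing ranks one instruction above the other.

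**Size**

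- Inputs: one non-fatal ILD case in more than 275 exposed patients (Section 5.2); 40 planned patients (Section 13.2).
- Assumption: rate = 1/275 = 0.36%. The documents say more than 275, so the observed rate is slightly lower. The case was in a patient with NSCLC, and Section 5.1.2 shows that the exposed group includes patients with ADPKD and healthy volunteers.
- Expected ILD cases = 40 × 1/275 = 0.145.
- Exact (Clopper-Pearson) 95% limits for 1/275: lower = 1 − 0.975^(1/275) = 0.009%; upper solves (1−p)^275 + 275p(1−p)^274 = 0.025, giving 2.01%. Multiplied by 40: 0.004 to 0.80 expected cases.

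This counts ILD cases, not harm from the wording. Harm would also need a site to follow the table instead of Section 9.1.4.6. The documents give no rate of suspected ILD, so the number of work-ups cannot be estimated.

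**The case against.** The best defence is that the event-specific section governs. ILD is a listed event of special interest, Section 5.2 directs readers to Section 9.1.4, and Section 9.1.4.5 refers back to the table, so the two are meant to be read together. The List of Tables describes the dose table as covering related events by CTCAE grade, whereas Section 9.1.4.6 deals with the earlier stage, before CT. On that view the general no-action line was never meant to keep a patient on drug through an ILD work-up.

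This softens the conflict but does not remove it. The table is not silent on pneumonitis, leaving the specific section to fill the gap. It has its own pneumonitis line, with a later trigger and a weaker action.

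The defence is stronger on restart. A reader might infer that the protocol lets a site restart after Grade 3 pneumonitis within 21 days without the Medical Monitor. The documents do not support that. Section 9.1.4.6 refers further management to the Medical Monitor without limit of grade or time, and a restart decision is further management. Section 9.1.3 is also permissive and compels no restart. What remains is a missing carve-out and cross-reference in the Grade 3 cell.

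A reader might also infer that Section 9.1.4.6 bars rechallenge for good. That is not settled either. Section 9.1.3.2 describes withdrawal from study treatment as no further tesevatinib, but the Grade 4 QTc text in Section 9.1.4.3.1 adds *permanently* when it means that. The meaning of discontinuation in Section 9.1.4.6 is therefore open.

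**Conclusion.** The inconsistency at Grades 1 and 2 is real and should be corrected. The table differs from Section 9.1.4.6 in both trigger and action, and at Grade 1 it does nothing even for confirmed pneumonitis. The Grade 3 restart wording is a lesser point.

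The conclusion rests on the wording of the first-appearance row and on the absence of a precedence rule. The issue is one of low-frequency safety, at about 0.15 expected ILD cases under the 1-in-275 assumption. It has no bearing on PFS-6, power or sample size. Rarity limits its weight, but it does not justify leaving two different stopping instructions for a listed event of special interest.

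**What to change.** Bring the table into line with Section 9.1.4.6:

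- **Grade 2 cell:** replace the pneumonitis line with *For suspected pneumonitis/ILD of any grade, stop study drug, obtain high-resolution CT and consult the Medical Monitor (see Section 9.1.4.6).*
- **Grade 1 cell:** repeat the same line.
- **Grade 3 cell and Section 9.1.3 text:** add *The restart rule does not apply to suspected or confirmed pneumonitis/ILD; follow Section 9.1.4.6.*

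Do not add a rechallenge route after confirmed ILD. Whether confirmed ILD ends treatment permanently is the sponsor's clinical decision, and this edit should leave it where Section 9.1.4.6 leaves it. The Synopsis and Section 7.1 refer to Section 9.1.3 and need no separate edit.

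The cost is a protocol clarification touching three table cells and one sentence, plus a few missed doses when CT excludes ILD. The statistical analysis does not change.

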# 9.2. Study Drug Accountability and Patient Treatment Compliance

Drug accountability and patient treatment compliance will be assessed using drug dispensing and return records, and the patient's study diary. The principal investigator is responsible for ensuring adequate accountability of all used and unused study drug. While the principal investigator may delegate components of drug accountability tasks to documented designee(s) (e.g., pharmacist), the ultimate responsibility for drug control and accountability resides with the investigator. This includes acknowledgment of receipt of each shipment of study drug (quantity and condition) and the maintenance of patient dispensing records and returned study product documentation. Dispensing records will document quantities received from Kadmon and quantities dispensed to patients, including lot number, date dispensed, patient identification number, patient initials, and the initials of the person dispensing study drug. Reasons for deviation from the expected dispensing regimen also must be recorded.

At study initiation, the study monitor will evaluate and obtain a copy of each site's written standard operating procedure for study drug disposal/destruction in order to ensure that it complies with the requirements of Kadmon.

At the end of the study, following final drug inventory reconciliation by the monitor, the study site will dispose of and/or destroy any remaining unused study drug supplies, including empty

containers, according to institutional procedures for destruction, reviewed and approved by Kadmon prior to material destruction. If the site cannot meet the requirements of Kadmon for disposal, arrangements will be made between the site and Kadmon or its representative, for destruction or return of unused study drug supplies.

All drug supplies and associated documentation will be periodically reviewed and verified by the study monitor over the course of the study.

# 9.3. Concomitant Medication and Treatment

If the patient must use a concomitant medication during the study, it is the responsibility of the principal investigator to ensure that details regarding the medication are recorded on the eCRF.

Patients should avoid ingesting grapefruit, pomelo or Seville orange fruits (and juice) with tesevatinib or at any time during the study. Patients should not take medications that are associated with a risk of QTc interval prolongation and/or torsades de pointes. Additionally, patients are not permitted to take concomitant medications that strongly inhibit (e.g., ketoconazole, itraconazole, erythromycin, clarithromycin) or induce (e.g., phenytoin, carbamazepine, rifampicin, or phenobarbital) the CYP3A4 isozyme. Steroid medications are allowed.

Administration of acid-reducing medications should be avoided during the study as these agents may decrease exposure to tesevatinib. If acid-reducing agents are needed, H-2 antagonists or antacids will be recommended rather than proton pump inhibitors. Administration of acid-reducing agents such as H-2 antagonists or antacids, if required, should take place no less than 2 hours before or after dosing with tesevatinib.

Since tesevatinib is a potent inhibitor of MATE transporter proteins, increased levels of concomitant medications that are secreted by the kidney proximal tubule cells into the renal tubule by MATE transporter proteins may occur. Thus subjects taking cephalexin, cimetidine, dofetilide, fexofenadine, metformin, procainamide, and pyrimethamine should be monitored carefully (see Appendix 4).

Other prohibited treatments include the following:

- Other investigational drugs
- Concurrent anti-tumor therapies such as chemotherapy, gene therapy, biologics, radiation therapy, or other immunotherapy
- Warfarin or other anti-coagulant drugs (Low dose low molecular weight heparin given for deep vein thrombosis (DVT) prophylaxis is allowed)
- Medications known to moderately or severely inhibit the CYP3A4 isozyme or any drugs that are moderate or severe CYP3A4 inducers. A stable regimen (≥ 4 weeks) of antidepressants of the SSRI class is allowed (common SSRIs include escitalopram oxalate, citalopram, fluvoxamine, paroxetine, sertraline, and fluoxetine)

• Drugs associated with torsades de pointes or known to prolong the QTc interval, including anti-arrhythmic medications within 2 weeks prior to Day 1 of treatment on study

Antiemetics and antidiarrheal medications should not be administered prophylactically before initial treatment with study drug. At the discretion of the investigator, treatment of symptoms with antiemetic and antidiarrheal medications may be undertaken per standard clinical practice.

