### 9.3.3. Interaction of Tesevatinib with Other Medications

Cytochrome P4503A4 is the major metabolic pathway of tesevatinib in humans. This suggests the potential for other drugs to significantly affect the biotransformation of tesevatinib in humans through drug-drug interactions. There is also a moderate potential to inhibit CYP2C8, CYP2D6 and CYP1A2 although this is most likely to occur at higher concentrations than those expected in this study.

Due to these interactions and potential interactions, inhibitors and inducers of CYP3A4, CYP2C8, CYP2D6, and CYP1A2 should be avoided if a substitute is available or otherwise used with caution in all patients while receiving study drug. In addition, patients must be closely monitored for the desired drug effect and potential AE.

Substrates of isoenzymes CYP3A4, CYP2C8, CPY2D6 and CYP1A2 may be used with appropriate clinical monitoring.

See Appendix 4 for a list of drugs that are clinically relevant inhibitors and inducers of CYP3A4, CYP2C8, CYP2D6, and CYP1A2.

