# APPENDIX 4. CONCOMITANT DRUGS THAT SHOULD BE AVOIDED, SUBSTITUTED OR USED WITH CAUTION

Drugs with QTc risk should be avoided per Section 9.3.3.1 of the protocol. Drugs that inhibit or induce the CYP isoenzymes 3A4, 2C8, 2D6, 1A2 should be substituted when possible or used with caution in view of their potential to alter tesevatinib exposure. Drugs that are secreted by the kidney proximal tubule cells into the renal tubule by MATE transporter proteins should be used with caution. This list is not comprehensive, and all concomitant medications should be evaluated for possible interactions with tesevatinib. See the Indiana University P450 drug interaction table for complete information (http://medicine.iupui.edu/clinpharm/ddis/main-table/).

Drug Type	Drugs with QTc Risk: AVOID	Drugs with CYP or MATE Interaction Risk: CAUTION
Anti-anginal	bepridil	
Anti-arrhythmics	amiodarone, disopyramide, dofetilide, ibutilide, procainamide, quinidine, sotalol	amiodarone, quinidine, dofetilide, procainamide
Antibiotics/anti-fungals	clarithromycin, erythromycin, azithromycin, sparfloxacin, gatifloxacin, moxifloxacin, troleandomycin, pentamidine	fluoroquinolones, clarithromycin, erythromycin, rifampin, rifabutin, terbinafine, itraconazole, ketoconazole, cephalexin, pyrimethamine
Anti-depressant		fluvoxamine, bupropion, fluoxetine, paroxetine, duloxetine, clomipramine, doxepin, nefazodone
Anti-epileptics		carbamazepine, phenytoin, phenobarbital
Anti-malarial	chloroquine, halofantrine, quinidine	quinidine,
Anti-nausea/emetics	domperidone, droperidol	
Anti-platelet		ticlopadine,
Anti-psychotic	haloperidol, mesoridazine, thioridazine, chlorpromazine, pimozide	aripiprazole, haloperidol,
Anti-viral		efavirenz, indinavir, nelfinavir, ritonavir, nevirapine
Asthma and allergy		chlorpheniramine, diphenhydramine, montelukast, fexofenadine
Calcium channel blockers		verapamil, diltiazem
CNS depressants		barbiturates
GI stimulant/heartburn/GERD	cisapride	cimetidine
Glucose lowering agents		Pioglitazone, troglitazone, metformin
Immune modulators		cyclosporine, tacrolimus
Lipid lowering		gemfibrazole,
Miscellaneous		St John's Wort, grapefruit juice, Seville oranges,
Opiates/dependence	levomethadyl, methadone	Suboxone, methadone

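### Protocol section 9.3 bars CYP3A4 inhibitors and inducers that section 9.3.3 and Appendix 4 allow with caution, and nothing says which rule governs

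*Protocol*

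**What the plan says.** Four places in the protocol set a ban during treatment.

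- Section 9.3, running text: "patients are not permitted to take concomitant medications that strongly inhibit (e.g., ketoconazole, itraconazole, erythromycin, clarithromycin) or induce (e.g., phenytoin, carbamazepine, rifampicin, or phenobarbital", with reference to the CYP3A4 isozyme. The eight drugs are given as examples.
- Section 9.3, bullet under other prohibited treatments: "Medications known to moderately or severely inhibit the CYP3A4 isozyme or any drugs that are moderate or severe CYP3A4 inducers", with an exception for a stable SSRI regimen.
- Synopsis, prohibited treatments: strong CYP3A4 inhibitors and strong inducers, with phenytoin named, the same SSRI exception, and a pointer to Appendix 4.
- Section 9.1.3.1, conditions for starting a new cycle: "no strong inhibitors or inducers of CYP3A4, CYP2C8, CYP2D6 or CYP1A2 (see Appendix 4".

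Two places set a softer rule.

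- Section 9.3.3: "inhibitors and inducers of CYP3A4, CYP2C8, CYP2D6, and CYP1A2 should be avoided if a substitute is available or otherwise used with caution". It adds close monitoring and also refers to Appendix 4.
- Appendix 4, lead-in: drugs that inhibit or induce these isoenzymes "should be substituted when possible or used with caution in view of their potential to alter tesevatinib exposure". In the table they stand under the column "Drugs with CYP or MATE Interaction Risk: CAUTION". The other column, headed AVOID, is for QTc risk.

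**The concern.** The same prescription can be forbidden by one section and allowed by another. A site that looks up phenytoin in Appendix 4 finds it under CAUTION. If the site judges that no substitute is available, 9.3.3 supports starting it. Section 9.3 does not permit it at all.

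Section 9.3.3 describes CYP3A4 as the major metabolic pathway of tesevatinib. The consequences differ by drug class:

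- **Inhibitors.** Ketoconazole or itraconazole would be expected to raise exposure in patients already dosed at the 300 mg daily MTD (section 5.1.2). Section 5.2 reports that QTc prolongation increased with plasma concentration.
- **Inducers.** The issue is altered exposure, not QTc. It bears on the consistency of treatment in a single-arm activity trial and on the plasma samples meant for exposure-response work (section 12.1.13).

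There is also a reporting consequence. The same use is a deviation under 9.3 but can be read as compliant under 9.3.3, so sites may record it differently.

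**Working it through.** The plan states no figure on this point and none has to be reproduced. The check is a cross-reading.

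**Step 1. Place the eight drugs named in 9.3 in Appendix 4.** Rifampicin in 9.3 is read as rifampin in the appendix. The relevant CAUTION cells are "fluoroquinolones, clarithromycin, erythromycin, rifampin, rifabutin, terbinafine, itraconazole, ketoconazole, cephalexin, pyrimethamine" (antibiotics and anti-fungals) and "carbamazepine, phenytoin, phenobarbital" (anti-epileptics).

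| Drug named in 9.3 | Role in 9.3 | AVOID (QTc) | CAUTION |
|---|---|---|---|
| ketoconazole | inhibitor | no | yes |
| itraconazole | inhibitor | no | yes |
| erythromycin | inhibitor | yes | yes |
| clarithromycin | inhibitor | yes | yes |
| phenytoin | inducer | no | yes |
| carbamazepine | inducer | no | yes |
| rifampicin (rifampin) | inducer | no | yes |
| phenobarbital | inducer | no | yes |

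- Under CAUTION: 8 of 8.
- Also under AVOID: 2 of 8, on QTc grounds.
- Under CAUTION only: 8 − 2 = 6, made up of 2 of 4 inhibitors and 4 of 4 inducers.
- Anti-epileptic row: 3 of 3 entries are drugs that 9.3 names as not permitted.

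By exact spelling the count would be five, with rifampicin absent from the appendix.

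**Step 2. Look for a carve-out.** Neither 9.3.3 nor the Appendix 4 lead-in excepts drugs barred by 9.3. No section says which text prevails.

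**Step 3. Follow the cross-references.** The synopsis ban and the 9.1.3.1 check both point to Appendix 4. The appendix gives no strength ratings, so a site cannot tell from it which entries are strong. The safeguard at each new cycle therefore leans on the table that carries the softer label.

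**Step 4. Compare the strength thresholds.**

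| Text | CYP3A4 agents barred on study |
|---|---|
| Synopsis | strong |
| 9.3, both statements together | strong and moderate |
| 9.1.3.1 | strong |

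A moderate CYP3A4 agent is prohibited by 9.3, but it falls outside the synopsis ban and passes the 9.1.3.1 check.

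**Step 5. Locate the window.** Section 9.1.3.1 applies at the start of each new cycle and a cycle is 28 days (section 9.1.2), so a drug started just after one check could run for up to about 28 days before the next. In Cycle 1 the window is shorter, because concomitant medications are also assessed at Day 15 (section 12.2.3).

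**The case against.** The best defence is that the texts can be reconciled. Section 9.3 is a specific ban, while 9.3.3 and Appendix 4 are general guidance for four isoenzymes and all strengths, so the specific rule should win. Section 9.3.3 allows caution only when no substitute exists and requires close monitoring. Appendix 4 describes itself as not comprehensive. A site that reads the synopsis, 9.3 or 9.1.3.1 meets a ban. The Medical Monitor confirms eligibility (section 7.1), ECGs are scheduled, and section 11.5 gives particular attention to interacting drugs.

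Much of this stands, and it limits the risk. It does not remove the conflict. Precedence of the specific rule is an inference that the protocol never states, and the ban texts themselves send sites to the softer table. ECGs and safety review act after the drug has been started.

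Four stronger readings are tempting and are not supported:

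- **That 9.3 contradicts itself on strength.** Its two statements are cumulative: the bullet adds moderate agents to a ban on strong ones. The mismatch is between 9.3 as a whole and the narrower synopsis and 9.1.3.1.
- **That the two-monthly visits after Cycle 24 leave a much longer unchecked window.** The 9.1.3.1 conditions attach to each new cycle, not each visit, and that schedule applies only to patients who have completed 24 cycles.
- **That entry is fully sealed by exclusion criterion 15.** That criterion turns on what the investigator judges likely to interfere or add risk, and it also refers to Appendix 4. It helps at entry but is not an unconditional bar.
- **That the SAP needs a new deviation rule.** SAP section 3.4 already has all deviations identified and classified before database lock. Once the protocol says that 9.3 governs, the classification follows.

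**Conclusion.** The point holds as a contradiction between stated rules on concomitant CYP3A4 agents. Six of the eight drugs that 9.3 names as not permitted are labelled only CAUTION in Appendix 4. Section 9.3.3 offers a conditional route to using them, and precedence is not stated. The count of six assumes that rifampin and rifampicin are the same drug. It leaves out erythromycin and clarithromycin because they also stand under AVOID. That treatment is generous to the plan, since section 9.3.3.1, to which the AVOID rule refers, still allows QT-prolonging drugs when clinically necessary after contact with the Medical Monitor.

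The practical exposure is mainly a barred drug started between new-cycle checks, together with uneven recording of deviations. The documents give no basis for the number of patients affected or the size of the change in exposure, so neither is estimated here. A reader might infer that the primary PFS-6 result is compromised. The documents do not support that: no sample-size or power figure in section 13.2 depends on this wording. The correction is worth making for safety and consistent exposure.

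**What to change.** Amend the protocol text in three places.

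1. **Precedence.** Add to 9.3.3 and to the Appendix 4 lead-in that the permission to use with caution covers only agents not prohibited by 9.3 or 9.1.3.1, and that 9.3 governs. This sentence alone resolves the main conflict.
2. **Appendix 4 table.** Flag the drugs named in 9.3 as prohibited. State that the flagged list is not exhaustive and that any other agent meeting the 9.3 threshold is also prohibited. Without that statement, flagging a few drugs could suggest that other strong agents under CAUTION are allowed, since 9.3 gives its drugs only as examples.
3. **Threshold.** Have the sponsor choose one CYP3A4 strength threshold for the on-study ban and use it in the synopsis, both statements in 9.3, and 9.1.3.1. Keep the stable-SSRI exception.

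The cost is a text amendment with IRB submission and approval under section 16. It needs no new visits, data or patients, and no change to the SAP.
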